5.3 Pregnancy

A limited amount of data from the use of metformin in pregnant women does not indicate an increased risk of congenital abnormalities. Risks concerning pregnancy within the study are chiefly due to radiation exposure from repeat CT scans. Study participants which are women of childbearing potential are required to use birth control methods that can achieve a failure rate of less than 1% per year when used consistently and correctly. This includes; combined (estrogen and progestogen containing) hormonal contraception associated with inhibition of ovulation, progestogen-only hormonal contraception associated with inhibition of ovulation intrauterine device, intrauterine hormone-releasing system, bilateral tubal occlusion, vasectomised partner and sexual abstinence. A postmenopausal state is defined as no menses for 12 months without an alternative medical cause. After enrolment into the study, pregnancy test for women with childbearing potential will be performed at clinical suspicion only. In case of pregnancy the study participant will be withdrawn from the study and, if possible, be seen and assessed by an investigator and asked to perform completion outcome measures except CT scan due to radiation exposure.

5.4 Insurance

All patients in the trial are covered by the patient insurance according to the Patient Injury Act.

6. ETHICAL CONDUCT OF THE STUDY

The study will be conducted in accordance with the protocol, applicable regulatory requirements, GCP and the ethical principles of the Declaration of Helsinki as adopted by the 18th World Medical Assembly in Helsinki, Finland, in 1964 and subsequent versions.

6.1 Ethics and regulatory review

It is the responsibility of the Sponsor to obtain approval of the study protocol/protocol amendments, the patient information and the Informed Consent from the ethical review board and regulatory authority before enrolment of any patient into the study.

The written approval from the ethical review board should be dated and have an attached list of those persons (with names and positions) present at the meeting.

The Sponsor shall report all serious and unexpected AEs to the ethical review board. If a study stops prematurely at a study centre for any reason, the ethical review board must be informed. At the end of the study, the Sponsor should notify the ethical review board.

The Sponsor should file all correspondence with the ethical review board.

6.2 Informed consent

It is the responsibility of the investigator to provide each patient with full and adequate verbal and written information about the objectives, procedures and possible risks and benefits of the study. All patients should be given the opportunity to ask questions about the study and should be given sufficient time to decide whether to participate in the study. The written patient information must not be changed without prior discussion with the Sponsor.

The patients will be notified of their voluntary participation and of their freedom to withdraw from the study at any time and without giving any reason. Patients must also be informed that withdrawing from the study will not affect their future medical care, treatment or benefits to which the patient is otherwise entitled.

The Investigator is responsible for obtaining written Informed Consent from all patients prior to enrolment in the study.

The patients will consent to:

- Participating in the study.
- Personnel concerned at regulatory authorities to gain full access to hospital records, to control the data collected in the study.
- Recording, collection and processing of data and storing of data in a database.
- Collection of blood for analysis and storage in a biobank.
- Possible transfer of information from the study to countries outside the European Union (EU).

It should be clearly stated that the data will not identify any patient taking part in the study, in accordance with the EU General Data Protection Regulation (GDPR).

A copy of the patient information and the Informed Consent form should be given to the patient. The Investigator (or the designated representative) who gave the verbal and written information to the patient shall sign the Informed Consent form. The Investigator should file the signed Informed Consent forms in the Investigator's File for possible future audits and inspections.

It is suitable to notify the patient's family doctor of the patient's consent to participate in the study.

6.3 Risks – Benefits

The uncertain knowledge state supporting the study-hypothesis emphasizes the importance of a risk assessment for each patient. A risk determination of potential risks in this study has been made. These risks together with the actions to minimize these risks are compiled below:

RISKS	ACTION
Suspected drug related adverse event, such as gastrointestinal events	If not tolerated, treatment with study drug should be reduced in dose or stopped, temporarily or permanent, and appropriate medical action should be initiated according to the nature and severity of the AE.
Patient require surgery or intravenous contrast media during study	Temporary discontinuation of the study drug according to clinical praxis for metformin. Typically 48 h after intravenous contrast media, in the perioperative phase and during fasting.
Patient develops suspect or manifest dehydration during study	If risk of dehydration for any reason the study drug is temporarily discontinued. This typically includes but is not limited to fever, serious infection, vomiting, diarrhoea and reduced fluid intake.
Patient develops suspect or manifest hypoxia during study	If risk of hypoxia for any reason the study drug is temporarily discontinued. This typically includes but is not limited to, sepsis, chock, myocardial infarction and decompensated heart failure.

Patient requiring continuous treatment with drugs that may temporarily affect renal function, such as NSAIDs	Study drug should be discontinued during treatment if there is evidence of renal impairment
Patient develops B12 deficiency secondary to metformin treatment BENEFITS	S-B12 levels are controlled every 24 months and replacement therapy is initiated if indicated

Other than obtaining an extensive medical evaluation and close monitoring of the AAA, no clear benefit was identified for the patients who participate in the study.

Table 2, possible risks and planned action

7. DATA MANAGEMENT

All data management will be handled by the investigator(s).

7.1 Monitoring of the study

In accordance with the principles of Good Clinical Practice (ICH GCP), monitoring of the study will be arranged by the Sponsor/PI. Three research nurses with formal training in monitoring according to ICH-GCP will monitor the study. During the study, the Monitor will have regular contacts with the study sites, including visits to ensure that the study is conducted and documented properly in compliance with the protocol, GCP and applicable regulatory requirements.

The extent of monitoring is described in a monitoring plan. The Monitor will ensure that accountability of investigational products is performed and will review source documents for verification of consistency with the data recorded in the eCRFs. The Monitor will also provide information and support to the investigators. The monitor will have access to all data in the eCRF, whereas investigators at each site only have access to data from their own site. The PI may access the data at all time.

Questionnaires, lab data, medical records and consent forms are source data stored in the investigator file as well as data entered directly in the eCRF and imaging.

The study centre may also be patent to quality assurance audit by the authorities. The investigators and other responsible personnel must be available during the monitoring visits and inspections and should devote sufficient time to these processes.

The investigators should provide curriculum vitae (CV) to be responsible for the study, as well as all personnel at the delegation list. All investigators and other responsible personnel should be listed together with their function in the study on the signature and delegation list.

7.2 Data management

Anonymised clinical data will be entered in an eCRF created in RedCap, provided by Uppsala University.

The investigator is responsible for ensuring the accuracy, completeness and timeliness of the data recorded in the eCRFs. The monitor will check the accuracy and completeness of the data reported in the eCRF's on a regular basis and before the database is locked.

The eCRF will be in accordance with the study specific Data Validation Plan (DVP). All inconsistencies detected during this procedure will be resolved through queries being issued to the investigational site. Any corrections made to entered data will be audited.

Data entered to the eCRF will be anonymised. Records of which e-code each patient is allocated will be kept locally at each site in a secure location.

All imagining will be reviewed anonymised by an operator blinded to treatment allocation.

8. STATISTICAL METHODS

All statistical analyses will be performed by the investigator(s).

8.1 Analysis set

All patients for whom a signed informed consent was obtained and an eCRF was started will be accounted for.

The Safety Analysis Set will include all patients who received at least one dose of study drug.

An intention-to-treat (ITT) analysis will include all randomised patients who received at least one dose of study drug and for whom at least one post dose observation for an efficacy endpoint is recorded.

The per-protocol analysis (PPA) consists of patients who sufficiently complied with the protocol. Inclusion in the PPA will require at least the following:

- An at least 80% compliance with the intended use will be accepted as per protocol.
- No major protocol deviations.

• Measure of primary efficacy endpoint at 60 months after baseline, and at 24 months for the interim analysis.

All efficacy analyses will be performed as both ITT and PPA. The ITT analyses is to be considered as main and the PPA as supportive.

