1.2.4 Safety objective

To determine adverse events; primarily related to known side effects of metformin and possible unexpected effects on AAA, related to metformin treatment after two and five years.

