2. STUDY PLAN AND PROCEDURES

2.1 Study design

The MAAAGI-trial is a population-based multi-center, prospective, parallel group, randomized, open label trial with blinded outcome assessment to assess if metformin up to 2g daily over a five-year period will reduce AAA growth in patients who do not have diabetes.

Patients will be recruited from a cohort of patients with diagnosed AAA at the following seven Swedish sites; 1) Uppsala University hospital, Uppsala, 2), Skåne University hospital, Malmö, 3) Gävle county hospital, Gävle, 4) Västerås county hospital, Västerås. 5) Karlstad county hospital, Karlstad 6) Falun county hospital, Falun, and 7) Umeå University Hospital, Umeå.

The patients should have a maximum aortic diameter of 30-49mm for men and 30-44mm for women, not have diabetes and be expected to tolerate metformin.

A total of 500 patients with AAA will be included in the study, 250 in each study arm. Patients will be randomised to metformin or standard care in a 1:1 ratio.

The patients are scheduled for one enrolment visit, eight study visits and ten phone contacts for those randomized to metformin (three to support titration of study drug) and seven phone contacts for those randomized to standard care. The study visits will take place at the vascular laboratory at the respective surgical departments for clinical examination and blood sampling and at the CT units at the radiology departments where CT-imaging will be performed.

After a run in phase to support titration of metformin, visits and phone contacts are scheduled to alternate every three months until 24 months and twice yearly thereafter. CT imaging and AAA US will be performed at baseline, 24 months and end of study, as well as if necessary according to clinical routine. Study drug will start at baseline and continue through completion.

End of study is defined as 1) study completion at 60 months, or 2) discontinuation from study before that for any reason, for example due to AAA repair or patients will.

When all patients have completed the 24-month follow-up (including imaging) an interim analysis will be performed to assess for efficacy and safety; if there is no trend towards a positive effect or signs of a harmful effect of metformin, the study will be stopped at this phase.

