The study will be performed in accordance with the ethically acceptable principles that have their origin in the Declaration of Helsinki and according to national legislations and international regulations. In addition, the study will be performed in accordance with this study protocol.

	Enrolment	Baseline/ Visit 1	Phone 2*	Phone 3*	Phone 4*	Phone 5	Visit 6	Phone 7	Visit 8	Phone 9	Visit 10	Phone 11	Visit 12	Phone 13	Visit 14	Phone 15	Visit 16	Phone 17	Completion
Visit window		$Day 0^{l}$	2 weeks	4 weeks	6 weeks	3 months	6 months	9 months	12 months	15 months	18 months	21 months	24 months	30 months	36 months	42 months	48 months	54 months	60 months
Informed consent	X																		
In- & exclusion criteria	x																		
Demographics ²	x																		
Smoking status	x						X		X		X		x		X		Х		X
Medical history	x																		
Current medication	x								X				x		X		Х		X
Physical examination ³	x												x						X
Vital signs ⁴	x						X		X		X		x		X		x		X
QoL questionnaires ⁵	x												x						X
CT scan		x											x						X
Blood samples ⁶	x								X				x		X		X		X
Randomisation		x																	
Ultrasound ⁷	x												x						X
Drug prescription*		x					X		X		X		x		X		Х		
Drug accountability*			X	X	X	X	X	X	X	X	X	X	X	X	X	X	х	X	X
Target dose of study drug*		X	X	X	X	X	X	X	X	X	X	X	X	X	X	X	х	X	
AE registration	X	X	X	X	X	X	X	X	X	X	X	X	X	X	X	X	х	X	х
SAE registration	x	x	x	x	x	X	X	X	x	X	X	x	x	x	x	X	x	x	X

Table 1. Overview of study activities. Phone 2-5 are to be performed +/- 5 days from target date and the remaining activities +/- 4 weeks from target date.

¹ Within four weeks of enrollment

² Demographics includes date of birth, sex and ethnicity

³ Physical examination includes cardio-pulmonary status and general appearance

⁴ Vital signs include blood pressure, heart rate, height (only at enrollment) and body weight

⁵ EQ-5D and RAND-36

⁶ Safety lab at all sites and blood samples for biobank at Uppsala and Malmö

⁷ Final Ultrasound +/- one week from CT scan

^{*} For those randomized to metformin only, see item 4.1.1 below

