4. STUDY CONDUCT

4.1 Treatment

The treatment allocation in this study will consist of;

- Study Arm 1; Metformin tablets taken orally with target dose of 2g daily
- Study Arm 2; Standard care as described in current AAA guidelines (Wanhainen 2019)

Standard care includes help with smoking cessation if applicable; encouragement of physical activity and a healthy diet; blood pressure control; statin and anti-platelet therapy treatment if the patient have clinical manifestations of atherosclerotic disease. Local guidelines dictate which classes of drugs are recommended and who is responsible for treatment and follow up. The study participants allocated to metformin receive standard care plus metformin treatment.

Patients will be encouraged to take metformin every day at similar times, preferably with a meal to minimize side effects.

Metformin is titrated stepwise to avoid gastrointestinal side effects. Starting dose is one tablet of metformin 500mg day 1-14, two tablets day 15-28, three tablets day 29-42 and four tablets daily from day 43 till the remainder of the study. If a patient misses one dose he/she is

encouraged to take one extra tablet with the following dose. No more than one dose should be compensated for if missed.

If a patient has severe side effects in the run-in phase, titration to target dose will be slowed. If a patient has severe side effects at the target dose, the target dose will be reduced to a level at which the side effects are tolerable and stay at this level for the remainder of the study. Target dose and compliance to this dose is recorded at each contact.

Table 2. Identity of investigational product(s)

Investigational product	Dosage form and strength	Study arm and time point
Metformin	Tablet 500mg, 1 daily	Study arm 1, Day 0-14
Metformin	Tablet 500mg, 2 daily	Study arm 1, Day 15-28
Metformin	Tablet 500mg, 3 daily	Study arm 1, Day 29-42
Metformin	Tablet 500mg, 4 daily	Study arm 1, Day 43-completion

Target dose of metformin 2g is chosen to reflect doses given in observational studies. It is predicted to be a sufficient dose to translate to a meaningful biologic effect whilst still safe and with acceptable side effects. The option to reduce the dose is expected to reduce drop-out rate. Once the final target dose is reached a different metformin tablet strength may be used for convenience, i e 1g rather than 500mg tablets.

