8.2.3 Safety variables

Safety variables include differences in drug related AE and GFR.

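### The Safety Analysis Set requires a dose of study drug, so as written it contains no standard-care patients and the randomised safety comparison is lost

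*Combined protocol and SAP*

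**What the plan says.** Section 8.1 (Analysis set) defines the safety population in one sentence: "The Safety Analysis Set will include all patients who received at least one dose of study drug". It has no clause for patients who are not given study drug, and no other section names a second safety population.

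Section 4.1 (Treatment) describes the control arm as "Study Arm 2; Standard care as described in current AAA guidelines". It adds: "The study participants allocated to metformin receive standard care plus metformin treatment". The product table in that section lists metformin for arm 1 and nothing for arm 2. In Table 1 (section 2.1) the rows for prescription, accountability and target dose carry the note "For those randomized to metformin only, see item 4.1.1 below". The design is a "population-based multi-center, prospective, parallel group, randomized, open label trial with blinded outcome assessment", so controls take no dummy tablet.

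Section 8.2.3 gives the safety outcomes in full: "Safety variables include differences in drug related AE and GFR".

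Safety data are not limited to one arm. In Table 1 the rows for blood samples and for AE and SAE registration have no metformin-only mark. Sections 5.1.1 and 5.2.9 schedule creatinine at enrolment and yearly. Sections 5.1.1 and 5.2.4 record AEs and SAEs at every contact.

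**The concern.** No standard-care patient can meet the dose condition. An analyst who follows 8.1 would describe safety in the metformin arm alone.

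Patients are aged 50-80 at entry and are followed for five years. Some loss of renal function and some illness will occur in that time whatever the treatment. In a single arm, a fall in GFR or a count of adverse events cannot be divided into a metformin part and a background part. The randomised control group would allow that separation, and its creatinine and adverse event data are scheduled anyway.

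The trial is open label, and section 8 says the investigators perform all the analyses. The safety population should therefore be correct in writing before the data are examined, and should not depend on an analyst departing from the plan. The first use may come early, because section 2.1 says the 24-month interim analysis covers safety as well as efficacy.

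**Working it through.** The plan gives no figure for the safety population or for GFR precision, so there is none to reproduce. The check applies the stated rule to each arm and then shows what a two-arm comparison could deliver.

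**1. Who qualifies under 8.1**

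- Planned patients: 500, with 250 per arm (section 2.1).
- Metformin arm: all can take a dose, so up to 250 qualify.
- Standard-care arm: no study drug and no placebo, so 0 qualify.
- Share of the trial excluded: 250/500 = 50%.

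**2. Whether other text brings controls back**

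- Section 8.1 says all patients with signed consent and a started eCRF will be accounted for. That is a statement about disposition and assigns no safety analysis to those patients.
- Section 8.1 assigns the ITT and per-protocol sets to the efficacy analyses only.
- Section 8.3 says laboratory data get descriptive and inferential statistics, but names no population.

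None of these admits controls to the Safety Analysis Set.

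**3. What *differences* means in 8.2.3**

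- In 8.2.1, and in items 1, 2 and 4 of 8.2.2, a change over time is marked by an explicit reference to baseline. Section 8.2.3 has no such reference.
- Item 5 of 8.2.2 (surgery and rupture) also speaks of a difference without naming baseline, and there only a between-arm meaning is possible.
- Adverse events have no baseline value to subtract.

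Between-arm is therefore the natural reading, though it remains an inference.

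**4. What the two-arm comparison could show (illustration)**

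The SD of GFR change is not in the documents; 8-12 ml/min is assumed. Section 8.4 plans for 30% dropout, which is applied here to GFR: 250 × 0.70 = 175 per arm.

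- SE of the difference = SD × √(2/n).
- Detectable difference at 80% power, two-sided 5% = (1.96 + 0.84) × SE = 2.8 × SE.

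| Assumed SD | SE, n = 175 | Detectable, n = 175 | Detectable, n = 250 (no loss) |
|---|---|---|---|
| 8 ml/min | 8 × √(2/175) = 0.86 | 2.4 ml/min | 2.0 ml/min |
| 12 ml/min | 12 × √(2/175) = 1.28 | 3.6 ml/min | 3.0 ml/min |

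The column for 175 is the relevant one, because the plan itself expects loss.

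**5. The one-arm alternative (illustration)**

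If GFR fell by an assumed 0.5-1.0 ml/min per year without any drug effect, the metformin arm alone would show a fall of 5 × 0.5 = 2.5 to 5 × 1.0 = 5 ml/min over 60 months. That is similar in size to the differences in step 4, and a single arm gives no means of separating the two.

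**The case against.** **The variable need not be a between-arm difference.** Section 8.2.3 does not say between groups, whereas 8.3 does for the primary endpoint, and neighbouring items use the same word for change from baseline. This stands as a limit: a reader might infer that the protocol expressly promises a between-arm GFR comparison, and it does not. It does not rescue the set, because a one-arm change over five years cannot isolate a metformin effect.

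**GFR is not formally tied to this set.** No section says GFR is analysed only in the Safety Analysis Set. The link comes from the set's name and evident purpose, and 8.3 would not forbid a comparison of laboratory data in all patients. This also stands. But no other population is given for safety, so the comparison would rest on the analyst's discretion.

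**A treated-only set suits drug-related events.** An event cannot be related to a drug that was not given, so the set is coherent for that variable taken alone. This is fair. It means the variable must be changed together with the set.

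**Aneurysm safety is compared elsewhere.** The safety objective (1.2.4) includes "possible unexpected effects on AAA, related to metformin treatment after two and five years", and a reader might infer that this too loses its control group. The documents do not support that. Growth is compared by treatment group in 8.3, surgery and rupture are efficacy variables in 8.2.2, and section 10 has its own harm criterion for growth and aneurysm-related events. None of these is assigned to the Safety Analysis Set.

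**It is the same slip as in the ITT definition.** The ITT sentence in 8.1 carries the same dose condition, with larger consequences. But section 4.2 partly counters it by keeping all randomised patients in their allocated group for ITT. No text does the same for the safety set, and correcting the ITT sentence would leave this one unchanged.

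**Conclusion.** The set definition is wrong as written: up to 250 metformin patients against 0 controls, in a trial that schedules the same creatinine and adverse event recording in both arms. That count needs no assumption beyond planned recruitment. That the safety variables are meant as between-arm differences, and that GFR belongs to this set, are reasonable inferences and not statements in the plan.

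The detectable GFR difference of about 2.4-3.6 ml/min rests on an assumed SD and on applying the planned 30% dropout to GFR. It shows only that the lost comparison would be informative.

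A reader might infer that control safety data will be missing, or that background decline will in fact be reported as a drug effect. Neither follows: the data are scheduled, and the wording can be corrected before any analysis. The point should be fixed, but it does not threaten the primary endpoint. The dose condition in the ITT sentence is a separate matter and needs its own correction.

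**What to change.** 1. **Section 8.1.** Redefine the Safety Analysis Set as everyone randomised to standard care, together with everyone randomised to metformin who took one or more doses.
2. **Section 8.2.3.** State that GFR, all AEs and all SAEs are compared between these two groups at 24 and 60 months. Use all events for the comparison, because drug-related has no clear meaning in the control arm.
3. **Section 5.2.4 and Table 1.** Section 5.2.4 describes event recording up to completion at 24 months, while Table 1 continues AE and SAE registration to the 60-month completion visit. Reconcile the two, since a 60-month comparison needs recording over the whole period.
4. **Interpretation.** Note that the metformin arm has ten phone contacts and the control arm seven. The three extra titration calls make early AE ascertainment unequal, which calls for caution in reading early events but does not justify leaving controls out.

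Cost: a sentence in each of 8.1 and 8.2.3 and a consistency correction to the event-recording period. No new visits or patients are needed, and no new data provided that events are recorded to 60 months as Table 1 schedules.

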4.1.1 Labelling

The study medication will be prescribed by the investigator and retrieved by the patient at the pharmacy. The prescription note will state that the drug is used for study purpose. The patients are being reimbursed for their study drug costs.

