4.1.3 Compliance

The patient is asked to note missed doses of medicine for any reason. The patient brings used bottles of metformin and receipts from the pharmacy at the study visit and remaining doses are counted to calculate compliance. Three consecutive days or more of missed medication are noted separately.

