4.2 Withdrawal from study

Patients may be discontinued from the study at any time, at the discretion of the investigator.

Patients are free to discontinue their participation in the study at any time for any reason.

Patients who discontinue from the study should always be asked about the reason(s) for the discontinuation (and informed about their right not to disclose their reason for doing so) and the presence of any adverse events (AEs). If possible, they should always be seen and assessed by an investigator and asked to perform completion outcome measures, including CT, US and QoL questionnaires. A pre-operative CT may be used for follow up should indication to operate the aorta arise. Adverse events should be followed up.

Study treatment should be stopped in the following cases: development of diabetes, persistent renal failure with GFR<45ml/min, severely deteriorating health, aortic surgery or onset of exclusion criteria.

If the study medication is stopped, patients will be asked to remain in the study and follow the other procedures according to the protocol. All randomised patients remain in the group they were originally allocated to for the purpose of intention-to-treat (ITT) analyses.

Patients who discontinue the study will not be replaced.

Sponsor has to be informed if a patient is withdrawn by any reason before study end. The "End of study" form must be filled out by the investigator and the reason should be stated.

The study number will not be reused if a patient is withdrawn.

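### The ITT set requires a dose of study drug, which controls never receive; waived for controls, the condition removes never-starters from the metformin arm only

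*Combined protocol and SAP*

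**What the plan says.** Section 8.1 defines the ITT analysis as covering "all randomised patients who received at least one dose of study drug and for whom at least one post dose observation" of an efficacy endpoint is recorded. The same section gives this set priority: "The ITT analyses is to be considered as main and the PPA as supportive". All efficacy analyses use it, so the 24-month interim analysis in section 10 does too.

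Only one arm can meet the dose condition. Section 4.1 describes the comparator as "Study Arm 2; Standard care as described in current AAA guidelines", with no placebo. In Table 1 (section 2.1) the rows for drug prescription, drug accountability and target dose carry the footnote "For those randomized to metformin only, see item 4.1.1 below". The design is a "parallel group, randomized, open label trial with blinded outcome assessment". On supply, section 4.1.1 says: "The study medication will be prescribed by the investigator and retrieved by the patient at the pharmacy".

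Two other sections bear on who is analysed. Section 4.2 states: "All randomised patients remain in the group they were originally allocated to for the purpose of intention-to-treat (ITT) analyses". Section 8.3 runs the primary analysis on patients who have a measured value at the time point and sets no dose condition.

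**The concern.** A set defined by receipt of study drug suits a placebo-controlled trial, where both arms have a first dose. Here it leaves the main analysis without a defined control group, and no section gives a control-arm equivalent of a dose or of a post-dose observation.

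The obvious repair in practice, waiving the condition for controls, creates an asymmetry. A metformin patient learns the allocation and must then collect the drug and take it. One who never does so but attends the CT is removed. The control patient who would have behaved the same way stays in. The analysis labelled ITT then compares starters with everyone, and the protection that randomisation gives is lost for that fraction of patients. If never-starters grow faster than others, the bias favours metformin; if slower, it goes against it.

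The condition is also unnecessary, because the supportive per-protocol set, with its 80% compliance threshold, already deals with patients who do not take the drug.

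**Working it through.** **Who qualifies, section by section**

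| Section | Requirement for the main analysis | Metformin never-starter with a CT | Control with a CT |
|---|---|---|---|
| 8.1, literal | dose and post-dose observation | out | out |
| 8.1, waived for controls | dose in the metformin arm only | out | in |
| 8.3 | measured value at the time point | in | in |
| 4.2 | randomised, kept in allocated group | in, or silent if it covers group assignment only | in |

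Neither 4.2 nor 8.3 cancels the dose condition. The imputations in 8.3 are for drop-outs and would not restore a never-starter who has a CT. Patients without a 60-month CT are outside the primary analysis on any reading.

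**The plan's own figure**

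Section 8.4 gives growth of 3 mm/year, SD 2.17, a 30% reduction (0.9 mm/year), 80% power and two-sided α 0.05. Per arm, 2 × (1.96 + 0.84)² × 2.17² / 0.9² = 91.3, so 92, or 184 in total. The stated 184 is reproduced.

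**Inputs for the size of the bias**

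- Evaluable per arm: 250 × 0.70 = 175 (30% dropout, section 8.4).
- SD: 2.17 × 1.10 = 2.39 to 2.17 × 1.15 = 2.50 (CT inflation, section 8.4).
- Assumed, not in the documents: *f*, the share who would never start (same in both arms); *d*, their difference in growth; *r*, their CT attendance relative to others (1, or 0.5, meaning 35% against 70%).

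**Formulas**

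- Share of such patients among evaluable controls: g = f·r / (f·r + 1 − f).
- Bias when they are dropped from metformin only: g × d.
- Metformin patients dropped: 175 × f × r.
- Type I error: two-sided 5% t test with no drug effect, no baseline adjustment, mean shifted by the bias.

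| f | d (mm/year) | r | Dropped | g | Bias (mm/year) | Type I error |
|---|---|---|---|---|---|---|
| 2% | 0.5 | 1 | 3.5 | 0.020 | 0.010 | 5.0% |
| 5% | 1.0 | 1 | 8.75 | 0.050 | 0.050 | 5.4% |
| 2% | 0.5 | 0.5 | 1.75 | 0.0101 | 0.005 | 5.0% |
| 5% | 1.0 | 0.5 | 4.4 | 0.0256 | 0.026 | 5.1% |
| 10% | 2.17 | 1 | 17.5 | 0.100 | 0.217 | 12.4–13.1% |
| 10% | 2.17 | 0.5 | 8.75 | 0.0526 | 0.114 | 7.0–7.1% |

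The first four rows are the main range. With equal attendance the bias there is 0.010/0.9 = 1% to 0.050/0.9 = 6% of the planned effect. The last two rows are an extreme corner, with *d* set to one stated SD. Moving one assumption to its extreme at a time, with r = 1, gives 6.9–7.0% (5% never start, 2.17 mm/year) and 6.5–6.7% (10%, 1.0 mm/year).

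A simulation of 100,000 null trials at SD 2.39 agrees. With never-starters dropped, type I error is 5.0%, 5.4% and 12.6% for r = 1, and 4.9%, 5.2% and 7.0% for r = 0.5. With all randomised patients who have a CT kept, it is 4.9–5.2% throughout.

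**Power if never-starters are kept**

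If the drug has no effect in never-starters, the effect is 0.9 × (1 − f). With 175 per arm:

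| f | Effect (mm/year) | Power, SD 2.50 to 2.39 |
|---|---|---|
| 0 | 0.90 | 92.0–94.0% |
| 2% | 0.88 | 90.9–93.1% |
| 5% | 0.86 | 89.2–91.6% |
| 10% | 0.81 | 85.7–88.6% |

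**The case against.** The strongest reply is that nobody would run the main analysis without controls. Sections 8.2.1 and 8.3 fix the comparison as metformin against standard care, and an analyst guided by 4.2 and 8.3 would keep never-starters with a CT. On that view this is ambiguity between sections, not a demonstrated exclusion. The numbers are also small and wholly assumed. A single tablet satisfies the condition, metformin patients are phoned at 2, 4 and 6 weeks, and the exclusion criteria in section 3.2 already screen out patients not expected to tolerate the drug or unlikely to comply. Never-starters may therefore be very few.

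Much of this stands. The bias is probably small, the extreme corner has no support in the documents and should not drive severity, and 8.3 does point towards inclusion. It does not remove the point. Section 8.1 is where the set is defined, and its dose condition is explicit. Waiving it for controls is the smallest departure from the text that makes the comparison possible, and that reading is the one-sided one. Section 8 assigns all analyses to the investigators, and blinding is stated only for image assessment. Membership of the main set should therefore not be left to interpretation once data are available.

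**Conclusion.** The concern holds and should be fixed. Taken literally, the main analysis set contains none of the 250 controls. On its workable reading, it excludes patients from one arm on behaviour that follows open allocation.

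In the main assumed range the consequence is a bias of at most 0.05 mm/year and a type I error of at most 5.4%, in a direction that cannot be known in advance. Those figures depend on a never-start rate, a growth difference and a CT attendance rate that the documents do not supply. The defect in the wording depends on none of them.

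**What to change.** Replace the ITT definition in section 8.1 with: *The ITT set includes all randomised patients, analysed as allocated, whether or not study drug was taken.* The observed-case restriction for the primary analysis is already in 8.3 and need not be repeated in the set definition. Patients without a CT then remain in the ITT set and can enter the imputation analyses. If an observation condition is nevertheless kept in 8.1, it should say post-baseline rather than post-dose, for both arms. It should also be made clear that the 8.3 sensitivity analyses still cover randomised patients without such an observation.

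A secondary point in the same section is that the Safety Analysis Set carries the same dose condition. If the differences named in 8.2.3 are between groups, 8.1 should say how controls enter that set.

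The cost is one or two sentences, with no extra patients or visits. Keeping never-starters dilutes the planned 0.90 mm/year to 0.86–0.88 at 2–5% never-starters (power 89–93%) and to 0.81 at 10% (power 86–89%), against 92–94% if everyone starts.
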